6.3 Subject Withdrawal Criteria

Subjects will be removed from the study for the following reasons:

- Subjects meet criteria for rescue (see section 6.4)
- Subjects withdrawal of consent
- Investigator decides it is in best interest of subject to withdraw from the study due to safety or efficacy issues
- Subject lost to follow up
- Study discontinuation by JD
-

An excessive rate of withdrawals can render the study uninterpretable: therefore unnecessary withdrawal of subjects should be avoided. A subject who withdraws for any reason should be encouraged to return to have the End of Treatment assessments performed. If a subject is lost to follow-up at any point during the study, attempts to contact the subject should be documented, and Subjective Symptoms Score should also be obtained. The reason for withdrawal from the study must be documented in the CRF by the Investigator.

If the subject withdraws from the trial and also withdraws consent for disclosure of future information, no further evaluation should be performed and no additional data should be collected. JD or DR may retain and continue to use any data collected before such withdrawal of consent.

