Assessment of Safety	
 Incidence of SPK at day 1 Incidence of SPK at Day 5 Intraocular pressure at Day 5 
VA loss of 4 or greater lines on Snellen VA Chart

Interim Analysis and Safety Monitoring	
 Safety data will be reviewed by [name], Medical Monitor and Sponsor. A summary report of the safety points will be created every 3 months, as well as the end of the study, and reported to the IRB.
Statistical Analysis	
The statistical analysis will evaluate: 1) The overall clinical success rate defined as the percentage of study participants achieving a clinical cure by Day 5 or an overall decrease in the sum of both grades by 3; 2) Microbiological cure rate defined as the percentage of study participants who demonstrate elimination of pre-treatment pathogen(s) by the Day 5 TOC exam.
 
A statistical difference in clinical cure rate will be defined where the 95% confidence limit for the difference in the two study groups (SCH1 vs. Placebo) is greater than (+/-)15%.
 
All data will be examined employing an “Intent to Treat” analysis for all patients. Mean outcome variables in the two study groups will be compared. Statistical means between both study groups will be analyzed by both parametric and non-parametric tests to allow for deviations of data from normal distributions.

Schedule of Visits and Assessments

	Screen / Visit 1	Visit 2	Visit 3
	Day 1	Day 3	Day 5
General Exams			
Informed consent	x		
Inclusion/exclusion criteria	x		
Medical history	x		
Vital signs	x		x
Physical Exam	x		
Patient comfort exam	x	x	x
AE assessment	x	x	x
Current meds	x	x	x
Ophthalmic exams			
BCVA	x		x
Visual acuity	x	x	x
Anterior segment slit lamp exam and tonometry	x	x	x
Dilated fundus exam	x		x

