6.4 Subject Rescue Criteria and Procedures

Subjects who experience onset of a corneal infiltrate, intraocular inflammation, or glaucoma are to receive rescue therapy. Dosing with SCH1/placebo is to be stopped at the time of administration of rescue therapy. All evaluations scheduled for visit 3/End of Treatment should be performed at this time.

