10.6.4 Eliciting Adverse Events

At each study visit the subject will be questioned about AEs. All AEs, whether observed by the Investigator, elicited by the Investigator or designee, or spontaneously reported by the subject will be documented in the subject's chart and the Adverse Event Reporting Form. The investigator must assess whether or not the AE is related to the study drug, and to determine whether to continue or discontinue the study drug.

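### Rescued subjects must leave the study, and others may be withdrawn for safety or efficacy, so their Day 5 assessment is early, optional or lost for reasons tied to the outcome

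*Combined protocol and SAP*

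**What the plan says.** **Removal.** Protocol section 6.3 lists the reasons for which subjects are taken out of the study. Meeting the rescue criteria is the first. Another is discretionary: "Investigator decides it is in best interest of subject to withdraw from the study due to safety or efficacy issues".

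**Rescue.** Section 6.4 ties rescue to new glaucoma, inflammation inside the eye or an infiltrate of the cornea. It states that "Dosing with SCH1/placebo is to be stopped at the time of administration of rescue therapy" and that "All evaluations scheduled for visit 3/End of Treatment should be performed at this time".

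**Other withdrawals.** Section 6.3 says "A subject who withdraws for any reason should be encouraged to return to have the End of Treatment assessments performed". No date is attached. Further evaluation is ruled out only for a subject who also withdraws consent to future disclosure.

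**Adverse events.** Under section 10.6.4 the investigator has "to determine whether to continue or discontinue the study drug". That section does not say that stopping drug ends participation.

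**Analysis.** The Synopsis lists SPK and intraocular pressure at Day 5 among the safety measures, and calls for an intent-to-treat "analysis for all patients. Mean outcome variables in the two study groups will be compared". Neither section 11.0 nor the SAP says how an early or missing Day 5 value is handled.

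**The concern.** The rescue criteria are themselves safety outcomes, and the discretionary route covers both safety and efficacy. Whether a subject has a true Day 5 assessment therefore depends in part on how that subject is doing. This is outcome-dependent missingness, and here a stated rule creates it; it does not arise only from subjects failing to attend.

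Two things are at stake. First, a Day 5 safety rate or mean may be computed on a reduced denominator, or on a mixture of Day 5 values and values taken when an event began. Second, the course of the eye between rescue and the end of the five-day period is not scheduled to be observed, although it bears directly on how the product's risk is judged. With 15 subjects per arm, one or two such cases are visible in the result.

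**Working it through.** **1. What happens to each kind of subject**

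| Situation | In the study? | Final-visit assessment |
|---|---|---|
| Stops drug for an AE, no more said (10.6.4) | Not stated to leave | As scheduled, by implication |
| Meets rescue criteria (6.3, 6.4) | Removed | Done early, at rescue |
| Withdrawn by investigator for safety or efficacy (6.3) | Removed | Encouraged, undated |

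Stopping drug and leaving the study are coupled by rule only in the second row. The third row is discretionary. No passage describes a rescued subject staying in the study off drug.

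**2. How much observation is lost.** Visits fall on Days 1, 3 and 5, with a window of one day either side for the last two. A subject removed before Visit 2 loses two scheduled visits, one removed at Visit 2 loses one, and one removed at Visit 3 loses none.

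**3. Effect on a Day 5 safety rate (illustration).** The documents give no AE or withdrawal rate, so the counts are assumed. Suppose 3 of 15 in an arm have a finding, and w of those three are removed and never assessed. The observed rate is (3 − w)/(15 − w).

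- w = 0: 3/15 = 20.0%
- w = 1: 2/14 = 14.3%
- w = 2: 1/13 = 7.7%
- w = 3: 0/12 = 0%

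If the early assessments are done, show the finding and are counted as Day 5, the rate stays 3/15 = 20.0% in every case.

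**4. Direction.** Take w = 1 and ask what a real Day 5 visit would have shown, assuming the other two still have the finding.

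- Finding persists: the true Day 5 rate is 3/15 = 20.0%. Omitting the subject understates it by 20.0 − 14.3 = 5.7 points; counting the early value is right.
- Finding has cleared: the true Day 5 rate is 2/15 = 13.3%. Omitting the subject overstates it by 14.3 − 13.3 = 1.0 point; counting the early value overstates it by 20.0 − 13.3 = 6.7 points.

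The error can go either way, depending on a handling rule and a later course that the plan leaves open.

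**5. Effect on the efficacy comparison.** The SAP states 87% power for 15 per arm, 20% against 80%, Fisher's exact test, 0.05 two-sided. Exact enumeration of the two binomials gives 87.2%, so the figure reproduces. Now let k SCH1 subjects be removed and compare two handling rules. Counting them as failures is modelled by lowering the 80% rate to 0.80 × (15 − k)/15.

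| k | SCH1 rate if counted as failures | Power, excluded | Power, counted as failures |
|---|---|---|---|
| 1 | 74.7% | 89.2% | 77.9% |
| 2 | 69.3% | 86.5% | 66.5% |
| 3 | 64.0% | 86.0% | 54.0% |

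The rise to 89.2% with one subject fewer reflects the discreteness of Fisher's test and is not a gain. The failure column assumes that removal is unrelated to cure, so it shows the larger cost; if removed subjects would have failed anyway, less is lost.

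**6. Is pressure measured at the rescue evaluation?** Section 7.2 lists slit lamp examination with tonometry at Visit 1, but slit lamp examination alone at Visit 3. The Schedule of Visits and section 10.3 include tonometry at every visit. Since the rescue evaluation borrows the Visit 3 list, it is unclear whether it includes pressure, even for a subject rescued for glaucoma.

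**The case against.** A reader might infer that any drug stop for a safety event removes the subject, that such subjects have no late safety data or recorded outcome, and that the Day 5 tables therefore look too favourable. The documents do not support this.

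- Section 10.6.4 keeps the drug decision separate from participation, and the discretionary item in 6.3 concerns leaving the study, not stopping drug.
- An end-of-treatment assessment is provided at rescue and sought after every other withdrawal. The reason for withdrawal must be entered in the CRF, data already collected are retained, and all AEs are documented.
- Section 10.0 defines the safety population by dose received, not by completion, and provides individual listings. An examination at the onset of an event would tend to capture the bad value.
- Removal does not take a subject out of the intent-to-treat set.
- Section 10.6.6, on serious adverse event reporting, was not available for this review, so nothing can be concluded about follow-up of serious events.

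All of this stands, and it limits the point. It does not answer three things: removal at rescue is mandatory, return after other withdrawals is optional and undated, and no rule says how early or missing values enter summaries fixed at Day 5. It is also fair that the period is short and few visits can be lost, which keeps the size of the problem down and makes it cheap to remedy.

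**Conclusion.** The point holds for subjects who are removed: those rescued, by rule, and those withdrawn for safety or efficacy, by discretion. Their Day 5 assessment is brought forward, optional or lost for outcome-related reasons, while the safety measures are tied to Day 5 and the analysis is meant to cover all patients.

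Each such subject is 6.7% of an arm (1/15). In the illustration, one unassessed subject moves a 20.0% rate to 14.3%, and none does so if the early assessment is made and counted. For efficacy, the handling of a single removed SCH1 subject separates 89.2% from 77.9% power. These figures rest on assumed counts. The documents do not establish that safety will look too good; the bias may run either way. This is an inexpensive improvement worth making, not a fault that invalidates the design.

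**What to change.** 1. In sections 6.3 and 6.4, separate ending study drug from ending study participation. Subjects who stop drug or are rescued, and who still consent, stay in the study and attend the remaining scheduled visits through Visit 3, in addition to the evaluation at the time of rescue.
2. Update any AE still open at those visits.
3. In the safety tables, report both the worst post-baseline value and the Visit 3 value for all dosed subjects in both arms, and label rescue-time values as such.
4. Reconcile 6.3, 6.4 and 10.6.4 with one another. Reconcile the Visit 3 list in 7.2 with the Schedule of Visits and 10.3, so that it is clear whether pressure is part of the rescue evaluation.

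When to stop drug or give rescue is left to the sponsor; the change concerns only what is observed and reported afterwards.

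The cost is amendment wording and at most one or two already scheduled visits for a few subjects. No sample-size input changes: 15 per arm still gives 87.2% power under the SAP's assumptions.

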6.4 Subject Rescue Criteria and Procedures

Subjects who experience onset of a corneal infiltrate, intraocular inflammation, or glaucoma are to receive rescue therapy. Dosing with SCH1/placebo is to be stopped at the time of administration of rescue therapy. All evaluations scheduled for visit 3/End of Treatment should be performed at this time.

7.0 Treatment of Subjects

Subjects meeting all the inclusion criteria and none of the exclusion criteria will be accepted into the study. Each subject must read and sign an informed consent form (or assent provided for pediatric subjects) prior to any screening procedures being performed. Subjects will be randomized either to placebo or SCH1, and will be followed in an outpatient setting. After their initial visit, subjects will come to the study center on day 3 and Day 5. Safety and efficacy measurements will be taken on these visits.

Potential risks and benefits to subjects participating in this study are detailed in the Subject Informed Consent Form.

7.1 Screening Prior To Randomization

A screening examination is performed on the initial visit. Screening procedures will include:

- Informed consent

- Inclusion/exclusion criteria

- Complete medical history and demographic information

- Best corrected visual acuity

- Slit lamp examination and tonometry

- Graded assessment of conjunctival inflammation and cornea

- Dilated fundus examination or Optos Fundus photography

- Conjunctival culture swab (A pre-packaged swab (*Visufarma Adenoplus*) to obtain a viral culture from the eye)

Documentation of the subject's fulfillment of the entry criteria for all subjects considered for the study and subsequently included or excluded is to be completed by the Investigator or designee. Documentation of screening failure details will be recorded in the source documentation.

7.2 Study Procedures/Assessments

The second visit has a +/- 1 day window. The third visit has a +/-1 day window.

Visit 1

Perform the following activities on Visit 1 (baseline)

- Review

- BCVA

- SLE and tonometry

- DFE

- Grading of injection / discharge

- Dispense study medication

Visit 2

Perform the following activities on Visit 2

- Record AEs

- Review of current medications

- Visual acuity

- SLE

- Grading of injection / discharge

Visit 3

Perform the following activities on Visit 3

- Record AEs

- Review of current medications

- Visual acuity

SLE
Grading of injection / discharge
DFE

8.0 Study Treatment

DR will provide SCH1 (the study drug) and identically packaged placebo (vehicle only). The SCH1 test article is an eyedrop suspension.

8.1 Storage and Handling

Study drug and placebo can both be safely stored at room temperature and ambient conditions for the duration of the trial. Study drug and placebo storage will be in locked cabinet with 24 hour alarmed temperature monitoring. Central storage and study package delivery will be coordinated by DR in concert with contract research and manufacturing organizations.

8.2 Study Drug Administration

The study drug is administered as one drop to the affected eye every two hours while awake on Day 1, four times per day while awake for Day 2 through Day 5. The drugs are administered by the patient.

8.3 Compliance

Compliance will be assessed by maintaining adequate drug dispensing and return logs. Patients will also keep written record of when treatments were given.

9.0 Assessment of Efficacy

Efficacy will be assessed by objective clinical score and microbiological culture.

9.1 Graded Measure of Conjunctival Discharge / Exudates

A three-point rating scale (0=absent, 1=mild, 2=moderate, 3=severe) will be employed to grade conjunctival discharge/exudates. Clinical efficacy will be defined as reduction in score by 2 grades (i.e. 3->1, 2->0) or a score of 0.

9.2 Graded Measure of Conjunctival Injection

A three-point rating scale (0=absent, 1=mild, 2=moderate, 3=severe) will be employed to grade conjunctival injection. Clinical efficacy will be defined as reduction in of each score to 0 or an overall reduction by 3 in the sum of both scores.

9.3 Other Assessments of Efficacy

Patients will keep a record of their own subjective symptom score from 1-5.

10.0 Assessment of Safety

The safety population is defined as all subjects who received one or more doses of SCH1. Standard summary and/or analysis techniques will be used for the evaluation of AEs, vital sign measurements, clinical laboratory results and physical examinations, and these are to be detailed within the body of the report. The safety data will be presented in individual listings and summary tables where appropriate.

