Eligibility Criteria	
Inclusion Criteria
 
 • Conjunctivitis (as defined below) within 72 hours of initial ocular symptoms. • At least 18 years of age. • Subjects capable of understanding the purpose and risks of the study, and able to give informed consent. • Conjunctivitis diagnosis defined as presence of the two cardinal signs of acute conjunctivitis- 1) bulbar conjunctival injection and 2) conjunctival discharge/exudates. • A three-point rating scale (0=absent, 1=mild, 2=moderate, 3=severe) will be employed to grade conjunctival discharge/exudates. • All patients will require a rating of 1(mild) or greater for conjunctival discharge/exudates. • Patients will require a rating of 1 (mild) for bulbar conjunctival injection.
	
Exclusion Criteria
 
 • Conjunctivitis greater than 72 hours after initial ocular symptoms • Corneal ulcer, endophthalmitis, or any other confounding infection of the eye • Patients taking topical anti-inflammatory medications on a chronic basis • Known steroid glaucoma responders • Active herpes ocular infection • Pregnant women • Known allergy to chlorhexidine
Trial Design	This is a phase II single-center, prospective, placebo-controlled, randomized study of SCH1 in the treatment of acute infectious conjunctivitis. Study drug will be evaluated against vehicle.
Primary Endpoint	Clinical cure defined as rating of 0/3 for bulbar conjunctival injection and 0/3 for conjunctival exudates/discharge or clinical success defined as an overall decrease by 3 in the sum of both grades.

Secondary	
 Patients will keep a self log of symptom score each of the 5 days of the study
Number of Subjects	
 30 (15 per treatment arm)
Target Population	
 Patients with infectious conjunctivitis defined by bulbar conjunctival injection (rated at least 1 on 3 point grading scale) and conjunctival exudates / discharge (rated at least 1 on 3 point grading scale). Patients greater than one year of age. Patients of any race or ethnic group.
Length of Study	
Enrollment period: 12 months Treatment period: 5 days Overall duration: 6 months 5 days

Study Drug	
Subjects will be randomized to one of the following treatment arms: Treatment Arm A: SCH1 Treatment Arm B: Placebo (Vehicle only)

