5.0 Trial Design

This is a Phase II single-center, double-masked, placebo controlled, randomized study of SCH1 for the treatment of infectious conjunctivitis. Approximately 30 subjects will be enrolled, who will be randomized in a 1:1 ratio between SCH1 and placebo. Subjects will be assessed at day 1, day 3, and day 5 for efficacy and safety.

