10.2 Corneal Epithelium Grading

Corneal epithelium grading, including the presence of SPK, will be recorded at each visit.

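### The safety population is defined by receipt of SCH1 alone, so read literally it omits the vehicle arm and conflicts with the synopsis's all-patient, two-group analysis

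*Combined protocol and SAP*

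**What the plan says.** Protocol section 10.0 sets the analysis set for safety: "The safety population is defined as all subjects who received one or more doses of SCH1". It then promises standard summaries of adverse events, vital signs, laboratory results and physical examinations, with listings and tables. No other section defines a safety population. The SAP covers clinical cure, descriptive statistics and sample size, and has no safety analysis.

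The trial has two arms. Section 5.0 describes subjects "who will be randomized in a 1:1 ratio between SCH1 and placebo", and the synopsis plans 15 per arm. The Statistical Analysis row of the synopsis applies an intention-to-treat analysis to all data and all patients and says the two groups will be compared.

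The Assessment of Safety row of the synopsis lists four items: "Incidence of SPK at day 1", "Incidence of SPK at Day 5", intraocular pressure at Day 5, and a visual acuity loss of four or more Snellen lines. Section 10.2 adds: "Corneal epithelium grading, including the presence of SPK, will be recorded at each visit". The visits are Day 1 (screening), Day 3 and Day 5.

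**The concern.** The definition turns on receipt of the active product. A subject allocated to vehicle, and given vehicle, receives no SCH1 and so falls outside the set. Tables built on that set would have one column.

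This matters because the disease itself can produce ocular findings. Section 2.1 says that both the infection and the immune response to it damage the eye. A corneal or acuity finding in an SCH1 subject may therefore come from the drug, the vehicle or the conjunctivitis, and the vehicle arm is what helps separate them.

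The second, smaller concern is the Day 1 SPK item. If Day 1 is the pre-treatment examination, its SPK incidence describes the patients at entry. Listed beside Day 5 without a label, it could be read as an early drug effect. The plan states no change-from-baseline analysis for SPK.

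**Working it through.** **The plan's own figure.** No figure is stated for safety. The one design figure that can be reproduced is the SAP's 87% power (Fisher's exact test, 15 per group, 20% against 80%, two-sided 0.05). Exact enumeration over Binomial(15, 0.2) and Binomial(15, 0.8) gives 87.2%. It agrees, but concerns efficacy and does not bear on this point.

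**Step 1: does SCH1 mean either product?** The synopsis names Arm A as SCH1 and Arm B as vehicle. Sections 5.0, 5.2 and 8.0 describe SCH1 and placebo separately. Where both are meant, section 6.4 says so: "Dosing with SCH1/placebo is to be stopped at the time of administration of rescue therapy". The literal reading of section 10.0 is therefore active arm only.

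**Step 2: how many subjects are left out?**
- Synopsis and SAP: 15 per arm, so 15/30 = 50%.
- Section 5.1 uses blocks of 4. Since 30 = 7 × 4 + 2, seven full blocks give 14 per arm and the last two subjects may fall either way, so each arm can hold 14 to 16.
- Section 11.0 speaks of 30 per group. On that figure 30/60 = 50%. The share is the same, but the two sample sizes need reconciling.

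**Step 3: is the definition consistent with the rest of the plan?**

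| Place | Who is covered |
|---|---|
| Section 10.0 | Recipients of SCH1 |
| Synopsis, Statistical Analysis | All patients, all data, two groups compared |
| Sections 7.0, 10.2, 10.3, 10.6.4 | Safety measured in subjects generally, with no restriction by arm |
| SAP | No safety population stated |

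The first two rows conflict. The third shows that vehicle data will exist.

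**Step 4: what would the corrected set support?** With about 15 against 15 and no events on placebo, the two-sided Fisher p-values are:
- 4/15 against 0/15: 2 × C(15,4)/C(30,4) = 2 × 1365/27405 = 0.100
- 5/15 against 0/15: 2 × C(15,5)/C(30,5) = 2 × 3003/142506 = 0.042

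The documents give no SPK rates. For assumed rates, exact Fisher power at 15 per arm is 33% (10% against 40%), 54% (10% against 50%) and 74% (10% against 60%). The comparison is descriptive.

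**Step 5: is Day 1 SPK a baseline value?** Section 7.1, headed Screening Prior To Randomization, includes the slit lamp examination and a corneal grading. Section 7.2 labels Visit 1 as baseline and ends its list with "Dispense study medication". Section 8.2 has patients give their own drops. The schedule has no second Day 1 visit. All four point to a grading made before the first dose, although no sentence states the interval between examination and first drop.

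**The case against.** The best defence is that the synopsis already covers the matter: all data, all patients, two groups compared. A statistician following that sentence would produce two-arm safety tables and treat section 10.0 as loose drafting. Part of this stands. A reader might infer from section 10.0 that the plan cannot compare safety between the arms, or that vehicle safety data are thrown away. The documents do not support either reading, because safety is measured at visits attended by both arms and the synopsis sentence is broad. But that sentence sits in a row whose named analyses are clinical success and microbiological cure, and it speaks of comparing means, whereas adverse events, SPK and acuity loss are counts. Section 10.0 is the specific rule for safety. The two places conflict, and neither clearly prevails.

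It can also be said that section 10.0 names adverse events, vital signs, laboratory results and physical examinations, not SPK, pressure or acuity, and that no section describes table columns. That is correct. Extending the restriction to the ocular items is an inference, though a natural one, since sections 10.1 to 10.4 fall under the same heading.

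A reader might also cite the upper confidence limit for 0 events in 15 as a measure of the harm: 1 − 0.05^(1/15) = 18.1% one-sided, or 1 − 0.025^(1/15) = 21.8% two-sided. It is not one. That limit belongs to the SCH1 arm and is the same with or without a vehicle column.

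Finally, the Day 1 SPK item does not block a comparison. Day 5 SPK and Day 5 pressure are post-dose, and a Day 1 value is useful as a reference. That objection stands in full, so Day 1 SPK is a labelling point and not a reason why arms cannot be compared.

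**Conclusion.** The definition in section 10.0 is wrong as written. Followed literally, it leaves out the whole vehicle arm (about 15 of 30 subjects; 14 to 16 with the stated blocks) and gives a safety population with no concurrent control, in conflict with the synopsis. It should be corrected before any safety table is built. The defect is confined to the analysis definition: data collection is sound in this respect and the primary efficacy analysis is untouched. Once corrected, the between-arm safety comparison is descriptive at this size.

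The Day 1 SPK item is a separate and lesser defect: a baseline value listed among safety outcomes without that label.

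The conclusion assumes that SCH1 in section 10.0 has the meaning it has elsewhere, that vehicle subjects are not given SCH1 by error, and that the text between sections 10.6.5 and 11.0, which was not in the copy reviewed, does not redefine the safety population. The pre-dose status of Day 1 SPK is a strong inference from the visit structure, not a stated fact.

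**What to change.** - **Section 10.0:** define the safety population as all randomised subjects who received at least one dose of SCH1 or placebo, analysed by treatment received and summarised by arm. The dispensing and return logs and the patients' dosing records in section 8.3 are enough to identify its members.
- **Synopsis, Statistical Analysis:** state whether the all-patient sentence governs efficacy only or safety as well, so that it agrees with section 10.0.
- **SAP:** add a short safety section with the same definition, by-arm summaries, and a statement that between-arm comparisons are descriptive.
- **Synopsis, Assessment of Safety:** keep Day 1 SPK but label it as baseline. Report new or worsened SPK at Day 3 and Day 5 relative to Day 1, by arm. Section 10.2 gives no corneal grading scale; if only presence is recorded, report new SPK alone.

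The cost is one sentence in section 10.0, small edits to the synopsis and a paragraph in the SAP. No new visits or data are needed, since SPK is already recorded at every visit.
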